5.3.2 Eligibility Criteria/Vulnerable Populations

Patients will be included in the study if they meet the following inclusion criteria:

- 1) adults older than age of 18
- 2) diagnosis a diagnosis of NF1;
- 3) permanently reside in the United States and
- 4) have pain interference aggregate scores of three or more in the last two weeks using the Brief Pain Inventory-Short Form (BPI-SF) scale.

Patients will be excluded if they: 1) have an undiagnosed case of NF1; 2) have documented major co-occurring psychiatric disease; 3) have moderate to severe cognitive deficits; or 4) have depression assessed using the Patient Health Questionnaire (PHQ-9) or anxiety assessed using the Generalized Anxiety Disorder scale (GAD-7) greater than or equal to the appropriate thresholds (10=mild major depression; 5=mild severe anxiety).

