5.2.2 Secondary and Exploratory Outcome Variables (if applicable)

Secondary Outcome Measures:

1. Treatment Services Review what are perceptions of satisfaction across groups exposed to the iCanCope mobile application using an The Treatment Services Review (TSR) [Time Frame: through the completion of the study, on average 4 months.]
2. Anxiety comparison within change of generalized anxiety measured by the generalized anxiety disorder scale (GAD-7). After reading each statement, one of four choices are provided and respondents can select one response (1=not at all sure, 2=several days, 3=over half days, 4=nearly every day). Each column is then added, and a total score is obtained, with scores falling into four levels of anxiety, including minimal (1-4), mild (5-9), moderate (10-14), and severe (15-21)[Time Frame: through the completion of the study, on average 4 months.]

3. Sleep functioning comparison within change of sleep quality measured by the PROMIS Sleep inventory. The higher the total score, the more severe the symptom. Total scores less than 24 suggest no to slight sleep disturbance, 24-28 suggest mild disturbance, 29-38 moderate disturbance, and greater than 38 severe sleep disturbance [Time Frame: through the completion of the study, on average 4 months.]
4. Short Form/Quality of Life the Short form survey 20- will measure quality of life across 8 subscales on respondent burden (Physical Functioning, Role-Physical, Bodily Pain, General Health, Vitality, Social Functioning, Role-Emotional, and Mental Health). Scores were transformed linearly to 0-100 scales, with 0 and 100 assigned to the lowest and highest possible scores, where high value indicated better functioning. [Time Frame: through the completion of the study, on average 4 months.]

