6.1.3 Selection of Instruments/Outcome Measures

In the pilot RCT, we plan to assess a broad range of subject characteristics, feasibility and clinical outcome measures over the course of the study. (See Table 1). Baseline assessments are designed to ensure that patients meet eligibility criteria and that important predictor treatment variables. Data will be self-reported and will be collected online and stored as per HIPAA privacy legislation. All measures have evidence of reliability and validity in adults in this age range, and include target specific measures of NF1 have recommended in previous trials

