6.4.3.2 Secondary Objectives Analyses, if applicable

Secondary analyses will explore three research questions: (1) Does smartphone program (*iCanCope-NF*) compared with control condition lead to differences in pain and pain-related activity limitations, sleep functioning, emotional functioning (depression, anxiety), pain catastrophizing, self-efficacy, knowledge, psychological flexibility immediately post-treatment (T2)? This will be evaluated by incorporating an estimating equation approach to understand the differences in scores and using a sequential multilevel logistic regression models to estimate the independent and combined effects of proposed time-varying (contextual) variables on the probability of pain levels. We will also test interaction effects between stable/trait-level participant characteristics and contextual variables. (2) Does the *iCanCope-NF + CM* increase the usage of the *iCanCope-NF* program as compared to *iCanCope-NF* without CM, and do their corresponding levels of pain and pain-related activity decrease? This will be evaluated between the two intervention groups and using the difference in nominal data sets, and simple qualitative analyses. (3) Do individuals with NF1 utilize the MBAA more readily because they are on the mobile application? To assess the moderation effect, we will include an interaction term for each separate moderator variable and key predictor of interest (two-way interaction between moderator and group for cross-sectional analysis and three-way interaction between moderator, group and time for longitudinal analysis) in the regression models and test its significance using Wald t-test.

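### Screening on GAD-7 below 5 leaves within-group GAD-7 change with little room to fall and an expected upward drift in every arm; a baseline-adjusted between-arm comparison should replace it

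*Combined protocol and SAP*

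**What the plan says.** Section 5.3.2 excludes people with depression or "anxiety assessed using the Generalized Anxiety Disorder scale (GAD-7) greater than or equal to the appropriate thresholds (10=mild major depression; 5=mild severe anxiety". The labels are garbled, but the number 5 and the direction (at or above) are legible.

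Section 5.2.2 lists among the secondary outcomes "Anxiety comparison within change of generalized anxiety measured by the generalized anxiety disorder scale (GAD-7". It codes the responses "1=not at all sure, 2=several days, 3=over half days, 4=nearly every day", says "Each column is then added, and a total score is obtained, with scores falling into four levels of anxiety", and prints the levels as "minimal (1-4), mild (5-9), moderate (10-14), and severe (15-21". The synopsis repeats this.

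Section 6.4.3.2, secondary question 1, compares the app with control immediately after treatment (T2) on several domains, including "emotional functioning (depression, anxiety". Of the method it says: "This will be evaluated by incorporating an estimating equation approach to understand the differences in scores".

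On timing, section 6.1.3 says "Baseline assessments are designed to ensure that patients meet eligibility criteria". Section 6.1.1 lists eligibility evaluation, consent and baseline assessment as separate items. It also names management of anxiety among the app's educational content.

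**The concern.** The same scale decides who may enter and then measures whether they improve. Two things follow.

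First, the people in whom the app's anxiety content could produce a visible fall are screened out, and those who remain sit near the bottom of the scale.

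Second, participants are selected for a low score at, or close to, the time point from which change is measured. Some of them are low that day by chance and will score higher next time whatever they receive. A within-group change therefore mixes any treatment effect with an upward drift.

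Read on its own, a rise in an app arm could be taken for harm. A null comparison with control could be taken to show that the app does nothing for anxiety, when the sample could show little improvement. The trial is a pilot meant to lead to a definitive trial (section 3.2), so either misreading could be carried forward.

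**Working it through.** **Inputs from the documents:** exclusion at GAD-7 of 5 or more (5.3.2); response codes 1 to 4, summed, with bands from 1 to 21 (5.2.2); 36 per group (6.4.2).

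**Assumed:** seven items, from the scale's name; and the mean, SD, retest correlation and SD for power given below.

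**1. Can the printed range be reproduced?**
- Printed coding, 1 to 4: totals run from 7 × 1 = 7 to 7 × 4 = 28. This does not give 1 to 21. No total lies below 5, so nobody would be eligible.
- Coding 0 to 3: totals run from 0 to 7 × 3 = 21. This matches the upper limit and every cut-point, except that the lowest total is 0, not 1.

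The printed coding, bands and threshold cannot all stand. The steps below use 0 to 21, the range that fits the bands.

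**2. Room to move.** Eligible totals are 0, 1, 2, 3 and 4.
- Largest fall for one person: 4 points.
- Possible rise: 21 − 4 = 17 to 21 − 0 = 21 points.
- The largest possible mean fall equals the baseline mean. For three illustrative distributions over 0 to 4:
  - weights 5:4:3:2:1 give (0 + 4 + 6 + 6 + 4)/15 = 1.33
  - equal weights give 10/5 = 2.0
  - weights 1:2:3:4:5 give (0 + 2 + 6 + 12 + 20)/15 = 2.67

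**3. Drift with no treatment effect.** As an approximation, expected change = (1 − r) × (unselected mean − mean of those selected). A simulation was run with a gamma-shaped score in whole points capped at 21, correlated retest, and selection on a score below 5. It gave a selected baseline mean of 1.8 when the unselected mean was 4.5, and 2.4 when it was 6.4.
- Mean 4.5: (1 − 0.8) × (4.5 − 1.8) = 0.54; (1 − 0.6) × (4.5 − 1.8) = 1.08
- Mean 6.4: (1 − 0.8) × (6.4 − 2.4) = 0.80; (1 − 0.6) × (6.4 − 2.4) = 1.60

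The simulated drift itself was +0.57 to +1.58 points, with 16% to 34% scoring 5 or more at retest. A rerun with a slightly different set-up (SD 4.5 to 5) gave 0.6 to 1.5 points and 15% to 35%. The drift was upward in every scenario.

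**4. Sensitivity of the between-arm comparison.** Power ≈ Φ(d / (SD × √(2/36)) − 1.96), two-sided 5%, no multiplicity correction.
- d = 1 point, SD 2: 1/(2 × 0.2357) = 2.12, power 56%
- d = 1 point, SD 3: 1/(3 × 0.2357) = 1.41, power 29%
- d = 0.5 point, SD 2: 0.5/(2 × 0.2357) = 1.06, power 18%

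A 1-point benefit is already about half of a baseline mean of 1.8 to 2.4.

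**5. Would a proportion at 5 or more be a better endpoint?** The 95% CI half-width for a difference is 1.96 × √(2p(1 − p)/36).
- p = 0.16: 1.96 × √0.00747 = 0.169
- p = 0.34: 1.96 × √0.01247 = 0.219

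That is 17 to 22 percentage points, too wide to serve as the main comparison.

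**The case against.** **Randomisation protects the comparison.** Question 1 in 6.4.3.2 is app versus control at T2. Regression to the mean acts on all arms alike and does not bias that contrast, and a benefit can appear as less worsening than control. This stands. It does not rescue the within-group change that 5.2.2 specifies, and it does not create room to fall.

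**Eligibility and baseline may be two measurements.** Section 6.1.1 lists them separately, and 6.3.3 describes a screening interview or self-report forms. If GAD-7 is taken twice, some baselines could be 5 or more, and part of the drift would occur before baseline. This stands as a condition. The sentence in 6.1.3 points the other way, though it is incomplete, and the sample would still be selected for low anxiety.

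**The magnitudes are assumed.** Correct. Only the 4-point limit follows from the cut-off and band-consistent scoring alone.

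Three stronger readings are tempting but not supported:
- A reader might infer that anxiety can only stay flat or worsen. That is true of the severity band, but no band analysis is planned. Section 6.4.3.2 speaks of scores, and a total of 1 to 4 can fall to 0.
- A reader might infer that the trial cannot answer its anxiety question. It can, with limited sensitivity.
- A reader might extend the point to depression through the PHQ-9 cut-off. PHQ-9 is not an outcome in 5.2.2, 7.7 lists it as a process measure, question 1 names no instrument for depression, and a cut at 10 leaves totals up to 9.

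**Conclusion.** The concern holds in limited form. With scoring that fits the bands, and if the screening score is the baseline, all participants start in the lowest band (or at 0). Individual totals can fall by at most 4 points and rise by 17 to 21. Within-group change is expected to drift upward by about 0.6 to 1.6 points in every arm under the stated assumptions. It therefore cannot be read as a treatment effect.

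The T2 comparison with control is not biased by this mechanism, but it has little room to show improvement. Other possible sources of bias are outside this point.

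The floor depends on item coding: under the printed codes nobody would be eligible, which is a separate inconsistency to resolve. One secondary outcome is affected. Engagement, pain severity and pain interference are not.

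**What to change.** - **Section 5.2.2 and synopsis:** replace within-group change for GAD-7 with a between-arm comparison of the T2 total score, adjusted for baseline GAD-7, reported as a difference with 95% CI. This agrees with question 1 in 6.4.3.2.
- **Supplement:** give the proportion at 5 or more at T2 by arm as description only.
- **Interpretation:** state in advance that a rise within an arm will not be read as harm, nor a null comparison as absence of an effect on anxiety. Limit anxiety conclusions to adults with NF1 pain who screened below the GAD-7 cut-off.
- **Timing:** say whether the eligibility GAD-7 is also the baseline value.
- **Reconcile** the response codes, the bands and the labelled threshold across the synopsis, 5.2.2 and 5.3.2. This review takes no view on which threshold is right.

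The cost is wording, with no added data or participants. The downside is small: a narrower stated population and a more modest anxiety claim.

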6.1 Intervention

6.1.1 Description of Intervention

Figure 1 presents a CONSORT study flow diagram. Potential participants will be required to access an online secure site to learn about the study and to be evaluated for eligibility, provide informed consent, and complete baseline assessments. Eligible participants will be randomly assigned to one of the 3 conditions: *iCanCope-NF*, *iCanCope-NF +CM*, or the Control Group (treatment as usual or TAU). Individuals in the *iCanCope* groups will receive 8 weeks of 24-hour access to the program.

The proposed architecture of the *iCanCope-NF* consists of four theory-based components, integrated across smartphone: self-monitoring (e.g. Real-time symptom tracking via patient self-report. Customizable graphs and reports; smart goal setting (e.g. Set

goals related to improving pain, sleep, mood, physical activity and social activity, Adherence to SMART' framework); personalized self-management instruction and rehearsal (e.g. (In-the-moment access to pain coping strategies, Personalized instruction based on goals); and detailed pain education (Provide information on types of pain, strategies for maintaining physical activity and strategies managing anxiety, stress and emotions).

iCanCope Orientation. At study intake, individuals within the *iCanCope-NF* and *iCanCope-NF* +Contingency Management (CM) groups will receive a 10-minute video orientation to the iCanCope program. The orientation will emphasize daily usage of the CBT treatment platform. Individuals will receive a login and password information, general information and instruction, and contact information for technical problems.

iCanCope-NF Group: In this group, individuals will receive the *iCanCope-NF program*. The intervention will be delivered on a restricted password-protected mobile application.

Participants will be encouraged to log onto the pain diary app (via automated alerts) once per day over the 8-week period to complete pain diary entries and develop and track their goals related to their pain, physical, social activities, sleep, as well as work through content based on their goals.

iCanCope-NF & CM Group: In addition to the *iCanCope-NF* activities outlined above, individuals will be rewarded with incentives such as points that are redeemable for prize-based gift card vouchers.[i] (#_edn1) Points will be accrued through access to new sections, daily check-ins, and engagement of the mobile application. Based on research, the total amount of money that can be earned by the patient over the course of the two months is 50 dollars USD. Individuals who are only randomized in the ICC-CM condition earn from \$1 to \$5 dollar amazon gift card per week for eight weeks (based on their usage). With an additional \$10 dollar gift card, if they check in every day. The total of the incentives can reach up to 50 dollars.

Control Group: The control group is designed to assess for potential effects on outcomes of time, attention, during the study. In addition to usual care, participants will be required to complete baseline and follow-up assessments similar to that of the intervention groups. They will be given that patient education, through preapproved flyers and information found from national websites regarding pain management, but no self-management strategies or opportunities for social support. They will not have access to the mobile application during the course of experiment; however, the control group will be offered the full *iCanCope-NF* program following the trial (T2) for a period of 2 months after the study is over.

6.1.2 Method of Assignment/Randomization

Participants will be randomized to one of the three conditions using an urn randomization algorithm which modifies ongoing randomization probabilities based on prior group composition groups, and controls for other predictive factors. This process greatly reduces experimenter bias and other internal validity threats to integrity. Gender be the only variable

that will be attempted to controlled for to ensure equal representation across the groups within the urn randomization using stratification.

6.1.3 Selection of Instruments/Outcome Measures

In the pilot RCT, we plan to assess a broad range of subject characteristics, feasibility and clinical outcome measures over the course of the study. (See Table 1). Baseline assessments are designed to ensure that patients meet eligibility criteria and that important predictor treatment variables. Data will be self-reported and will be collected online and stored as per HIPAA privacy legislation. All measures have evidence of reliability and validity in adults in this age range, and include target specific measures of NF1 have recommended in previous trials

6.1.4 Intervention Administration

Individuals assigned to the *iCanCope-NF*, *iCanCope-NF +CM* will have 8 weeks of 24-hour access to the program. Individuals assigned the Control will not have access to the *iCanCope-NF* application.

6.1.5 Reaction Management

Patients that have technical problems will be connected to the infrastructure team of the mobile application. Emergency Contact information will be provided within the mobile application (e.g. 911 services, National Suicide Hotline, and referring to their primary care office). Additional support will be provided to NF-community advocacy organizations for non-emergencies (NF Northeast, NF Network).

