6.3 Study Procedures

6.3.1 Study Schedule

A total of three visits (all virtual) will be completed. The three visits will consist of admission, discharge and follow-up. Admission for control group will consist of 30 minutes, while admission for individuals within the experimental groups, should take 60 minutes. Discharge evaluations for each should be 45 minutes (30 minutes for assessments, 15 minutes debriefing). Follow-up should be 30 minutes for assessments. Individuals who have access to the mobile application are encouraged to provide daily check-in evaluations (estimated time of 2 minutes) and utilize the different modules at their discretion. The participants will have free reign of the mobile application and are not required to spend any time on the mobile application. No other communication with the research team will take place between all participants and the time intervals previously mentioned. For individuals who are placed in the control group, they will be encouraged to utilize the materials found on several chronic pain websites, with no required time commitments. The mobile application will not remind or notify the participant if they have to login or input information.

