6.3.6 End of Study and Follow Up

At the end of the study, all participants in each group (TAU, iCanCope, iCanCope+CM) will be required to complete the identical set of assessments at intake, minus demographic information. Individuals who prematurely left early or who withdrawn from the study will not be asked to complete the end of the study survey. Additionally, individuals with access to the iCanCope mobile application license will end and will not be able utilize the mobile application until the follow-up is complete. For individuals who did not have access to the iCanCope mobile application they will continue not having access to the mobile application.

All participants in each group will complete a 6-week post discharge follow-up. The follow-up will be identical to the discharge evaluation. Individuals will be emailed a secured email by the research assistant to complete the survey one day before the 6-week survey. All participants will have a one-week (7days) to complete the assessment, and a reminder email will be sent on the last day of the survey to the participants. Individuals will not be required to complete but will be encouraged to do so.

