6.3.7 Removal of Subjects

In cases of psychological deterioration, we will recommend to patients to contact their physician immediately and consider withdrawing from the study to receive more intensive treatments. When necessary subjects will be withdrawn from this study and research staff will assist patients with appropriate sites for treatment such a physician, crisis center, or emergency room. The mobile application will also have emergency information available that can be tailored by each patient to provide specific contacts that they may need. In instances of suicidal or homicidal risk, appropriate authorities including their primary provider will be informed and necessary actions (seeking crisis/suicidality evaluations and possible hospitalization) taken.

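### The app is the only medium the visible protocol names for the emergency contact list, so controls lack it throughout the trial and app participants lose it at discharge

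*Combined protocol and SAP*

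**What the plan says.** Section 6.1.5 (Reaction Management) states that "Emergency Contact information will be provided within the mobile application" and gives emergency services, a national suicide line and the primary care office as examples. Its only other channel, the advocacy organisations, is for non-emergencies. Section 6.3.7 (Removal of Subjects) adds: "The mobile application will also have emergency information available that can be tailored by each patient".

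Access to the app depends on arm and period:

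- **Both iCanCope arms:** under section 6.1.4 they "will have 8 weeks of 24-hour access to the program". After discharge, section 6.3.6 says they "will not be able utilize the mobile application until the follow-up is complete". The follow-up is 6 weeks after discharge.
- **Control arm:** section 6.1.1 says "They will not have access to the mobile application during the course of experiment". Section 6.3.6 says that, after discharge, "they will continue not having access to the mobile application". Section 6.1.1 offers controls the "program following the trial (T2) for a period of 2 months after the study is over". The materials it lists for them during the trial concern pain management.

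On contact with staff, section 6.3.1 schedules three virtual visits (admission, discharge, follow-up) and says: "No other communication with the research team will take place between all participants".

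**The concern.** The protocol itself foresees psychological deterioration and suicidal or homicidal risk (section 6.3.7), and does so for patients in general, not just app users. The contact list is what a participant could use when staff are unaware of a problem. If the text is followed as written, the list reaches two of three arms, and those two only while they hold an app licence. The protocol gives no reason for tying it to allocation or for withdrawing it at discharge, and nothing in the design requires either. What is at stake is participant protection that differs by arm and period. No bias in the effect estimates is claimed.

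**Working it through.** The plan gives no figure for this, so there is none to reproduce. The check is person-time arithmetic.

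**Inputs**

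- 36 per arm, 3 arms, 108 in total (section 6.4.2).
- 8 weeks of app access in each of the two iCanCope arms (section 6.1.4).
- Follow-up 6 weeks after discharge, in all arms (section 6.3.6).
- No app for controls up to follow-up (sections 6.1.1, 6.1.4 and 6.3.6).
- Assumptions: discharge falls at the end of the 8 weeks, so the planned time is 8 + 6 = 14 weeks, and everyone is retained.

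**Formula**

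Share without app access = 1 − (person-weeks with access) / (total person-weeks).

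**Base case**

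- Total: 108 × 14 = 1,512 person-weeks.
- With access: 72 × 8 = 576.
- Without access: 1,512 − 576 = 936, made up of 36 × 14 = 504 in controls and 72 × 6 = 432 in the app arms.
- Share: 936 / 1,512 = 61.9%.
- By arm: controls lack access for 14 of 14 weeks (100%); app participants for 6 of 14 weeks (42.9%).

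Arm size cancels when the arms are equal: 1 − (2/3) × (8/14) = 61.9% for any n per arm.

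**Other readings of the timeline**

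| Reading | Calculation | Share without app access |
|---|---|---|
| 8 + 6 weeks | 936 / 1,512 | 61.9% |
| Adding the 7-day survey window (section 6.3.6), 15 weeks | 1 − 576 / 1,620 | 64.4% |
| Stated average of 4 months (section 5.2.1), 4 × 30.4375 / 7 = 17.4 weeks | 1 − (2/3) × (8/17.4) | 69.3% |
| Controls given the app at T2, taken as end of treatment, so 36 × 6 = 216 more person-weeks with access | 1 − (576 + 216) / 1,512 | 47.6% |

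The last row arises because T2 means immediately after treatment in sections 6.2.1 and 6.4.3, while section 6.1.1 uses it for the end of the trial. Section 6.3.6 contradicts that row, since it keeps controls off the app after discharge. The third row differs from the first because 14 weeks is 14 × 7 / 30.4375 = 3.2 months, not 4.

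**What the share measures**

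It is time without the app copy of the list. Section 6.3.7 also provides advice to contact a physician, staff help in finding a place of treatment, and informing authorities and the primary provider in cases of suicidal or homicidal risk. None of these is limited by arm or period, so the share cannot be read as time without any emergency route.

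**The case against.** The strongest counter-case is that the text does not confine emergency provision to the app.

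- Section 6.1.5 does not use the word *only*, and section 6.3.7 says the app will *also* hold the information, after describing staff routes open to every participant.
- Section 6.2.3 requires adverse events to be asked about at each visit, section 6.3.1 includes a debriefing at discharge, and section 7.12 has monthly safety review.
- Section 5.3.2 excludes documented major psychiatric disease and people at or above its depression and anxiety thresholds; section 7.12 rates the study minimal risk.
- The listed contacts are generic, and controls continue usual care.
- The consent pages were removed from the text reviewed, and the operating procedure mentioned in section 7.6 is not shown. Either could carry the contacts.

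Most of this stands as a limit on the claim. A reader might infer that emergency information exists nowhere but in the app, that controls never get it, or that 62% of follow-up is unprotected. The documents support none of these: the staff routes apply to all arms, section 6.1.1 offers controls the app afterwards, and absence from the consent form cannot be shown. Nor should the statement in section 6.3.1 be read as barring a participant from calling the team in an emergency; it describes planned contact, and the stricter reading would clash with section 6.3.7.

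What the objection does not remove is the gap between visits. The staff routes operate once staff know of a problem. With no planned contact between visits, that depends on a visit or on the participant getting in touch. A list in the participant's hands serves the time before that, and the visible protocol names no way to supply it to someone without the app.

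**Conclusion.** The point holds in a limited form. In the visible protocol the app is the only named medium for the emergency contact list; controls lack it during the trial, and app participants lack it from discharge until follow-up is complete. About 62% of planned person-time is without app access to the list, assuming 14 weeks, equal arms and full retention. The range is 64% to 69% on longer timelines, and 48% on a reading of control access that section 6.3.6 contradicts. The figure follows from the design and measures neither risk nor lack of all emergency provision. Confidence is moderate, because the consent form cannot be inspected. It is a low-cost safety improvement worth making and does not threaten the trial's validity.

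**What to change.** Reconcile sections 6.1.1, 6.1.5, 6.3.1, 6.3.6 and 6.3.7 on who holds the emergency contact list and when, including the meaning of T2 for control access. Then state in 6.1.5 and 6.3.7 that the list already prepared for the app is given to all three arms outside the app, at admission and again at discharge. If the consent form already does this, a cross-reference is enough. Keep the in-app copy, and leave every clinical action as the protocol has it.

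The cost is a one-page handout or survey text and a minor IRB amendment. The list contains no pain self-management material, so it should not affect the contrast between arms.
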